3.1. PRIMARY OBJECTIVES

To determine whether NBS guided 1Hz rTMS targeting the motor representation areas of hand muscles on the healthy brain hemisphere has a beneficial effect on the motor recovery of the corresponding stroke-affected muscles when combined with standardized task-oriented motor rehabilitation.

Primary outcome measure: Upper-extremity Fugl-Meyer score.

The beneficial effect of 1Hz NBS guided rTMS will be established if a statistically signicantly greater proportion of patients receiving NBS-rTMS attain clinically important improvement in the primary outcome measure than patients receiving sham-rTMS between baseline and 6 months post-treatment.

3.2 SECONDARY OBJECTIVES

Secondary outcome measures for the study are:

Absolute change in points on UEFM

Action-Research Arm Test (ARAT)

NIH Stroke Scale (NIHSS)

The changes on these scales between baseline and 6 months post-treatment will be determined for both therapy groups and the groups compared to each other to establish effects of therapy.

Quality of life outcomes:

In addition to the other secondary outcome measures above the patients' quality of life will be assessed using the EQ-5D questionnaire. The change on this scale between baseline and 6 months post-treatment will be determined for both therapy groups and the groups compared to each other to establish effects of therapy on quality of life.

Assessment of safety:

To assess safety of study device use, all Serious Adverse Events, Unanticipated Adverse Device Events and Device Related Adverse Events will be recorded and compared between therapy groups..

4.0 study design

This is a prospective multi-center sham-controlled double-blinded study.

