The beneficial effect of 1Hz NBS guided rTMS will be established if a statistically signicantly greater proportion of patients receiving NBS-rTMS attain clinically important improvement in the primary outcome measure than patients receiving sham-rTMS between baseline and 6 months post-treatment. Minimal clinically important improvement is defined as an increase of 5 points on the upper extremity Fugl-Meyer score [Page SJ, et al. 2012].

Secondary Assessments	1. Secondary outcome measures for the study are:					
and	Arm-Research Action Test (ARAT)					
Endpoints:	NIH Stroke Scale (NIHSS)					

Quality of life assessment: EQ-5D questionnaire.

The changes on these scales between baseline and 6 months post-treatment will be determined for both therapy groups and the groups compared to each other.

2. Safety endpoint

To assess safety of study device use, all Serious Adverse Events and Unanticipated Adverse Device Events and Device Related Adverse Events will be recorded and compared between therapy groups..

ABBREVIATIONS

APB	Abductor Pollicis Brevis
CRO	Clinical Research Organization

EDC	Extensor Digitorum Communis
EMG	Electromyography
FDA	Food and Drug Administration
fMRI	Functional Magnetic Resonance Imaging
IRB	Institutional Review Board
MEP	Motor Evoked Potential
MRI	Magnetic Resonance Imaging
MT	Motor Threshold
NBS	Navigated Brain Stimulation
NBT	Navigated Brain Therapy
rTMS	Repetitive Transcranial Magnetic Stimulation
SAE	Serious Adverse Events
SD	Standard Deviation
TMS	Transcranial Magnetic Stimulation

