A recent discovery is to use repetitive TMS to modulate regional excitability of the motor cortex (Hummel and Cohen, 2006). Two potential roles have been described for rTMS in stroke recovery: (1) inhibit, i.e., down-regulate, the non-lesioned side (using 1 Hz rTMS), or (2) excite the lesioned side (using 10 Hz rTMS). In the present study 1Hz rTMS will be utilized to down-regulate the non-lesioned hemisphere with the goal of improving response to motor training by reducing interhemispheric inhibition and potentially facilitating activity in the lesioned hemisphere.

Previously at least 27 studies on effects of contralesional 1Hz rTMS targeting the primary motor cortex on motor function utilizing varying rTMS protocols have been performed in 2598 patients with stroke in 2005-2016 [Boggio PS 2006, Mally J and Dinya E,2008, Dafotakis M 2008, Fregni F 2006, Khedr EM 2008, Kirton A 2008, Liepert J 2007, Mansur CG 2005, Nowak DA 2008, Takeuchi N 2005, Takeuchi N 2008(a), Takeuchi N 2008(b), Khedr EM 2009, Emera T, 2010, Kakuda W 2011 (a), Kakuda W 2011 (b), Thielig S 2011, Kakuda W 2011 (c), Kakuda W 2012, Sung W 2013, Abo M 2013, Higgins 2013, Kim, 2014. Rose 2014 Cha H 2015, Zheng C 2015, Kakuda W 2016].

Further, in a recent meta-analysis of 18 randomized controlled trials including a total of 392 patients, rTMS therapy was found to have a positive effect on motor function in patients with stroke (Hsu, 2012). This meta-analysis found a significant effect size of 0.55 for motor outcome (95% CI, 0.37–0.72). Further subgroup analyses demonstrated more prominent effects for subcortical stroke (mean effect size, 0.73; 95% CI, 0.44–1.02) and in studies that applied low-frequency (1Hz) rTMS (mean effect size, 0.69; 95% CI, 0.42–0.95). The meta-analysis concluded that rTMS has a positive effect on motor recovery in patients with stroke, especially for those with subcortical stroke.

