6.0 ANALYSIS PLAN

The results of functional motor tests at end of rehabilitation (5-10 days post treatment) and at 1, 3 and 6 months after the end of rehabilitation will be compared to the results obtained at baseline to determine the functional recovery if any that has occurred. The results of patients randomized into separate groups will be compared to each other to determine the effect of rTMS.

The primary analysis population will be the intent-to-treat (ITT) population. In addition, a separate analysis will be conducted on the per protocol (PP) population.

Primary outcome measure for the trial is the Upper-extremity Fugl-Meyer score.

The beneficial effect of 1Hz NBS guided rTMS will be established if a statistically significantly greater proportion of patients receiving NBS-rTMS attain clinically important improvement in the primary outcome measure than patients receiving sham-rTMS between baseline and 6 months post-treatment.

The size of the treatment effect will be measured by the odds ratio parameter which is defined as

$$OR = \frac{P_{TRT} / (1 - P_{TRT})}{P_{REF} / (1 - P_{REF})}$$

where P_{TRT} and P_{REF} denote the proportion of subjects with clinically significant change from baseline in Fugl-Meyer score, in the treatment and reference groups respectively.

The null hypothesis is H_0 : OR = 1 and the two-sided alternative hypothesis is H_1 : $OR \neq 1$.

The proportion of responders in each treatment group will be summarized, along with the estimated odds ratio, the 95% confidence interval for OR, and the Wald Chi-square test p-value. The primary analysis will be performed on the ITT, and on the PP population as a sensitivity analysis.

Secondary outcome measures for the trial are ARAT test, , NIHSS, and EQ-5D.

Descriptive statistics will be summarized by treatment and visit. Absolute difference (in points) in improvement will be summarized for both treatment groups between baseline and 5-10 days and 1, 3 and 6 month follow-up visits and the treatment groups compared via a two-way ANOVA.

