6.4 STRATA AND COVARIATES

The primary efficacy analysis will be stratified by length of time after stroke (3-6 months vs. 6-12 months).

Additional covariate analyses will model the primary endpoint (a binary response of UEFM score improvement), absolute changes (in points) in the tests of motor function (UEFM, and ARAT) using hours of occupational therapy outside the trial and overall hours of therapy (occupational, physical, and home exercise) as covariates during treatment phase and over the entire 6 months of follow-up.

All covariate analysis will be performed for both ITT and PP population.

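### UEFM change in points is a secondary outcome in section 3.2 but is missing from the lists in the protocol summary and section 6.0, and its main model is not clearly specified

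*Combined protocol and SAP*

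**What the plan says.** - **Section 3.2 (secondary objectives)** lists "Absolute change in points on UEFM" first, followed by ARAT and NIHSS, and then states: "The changes on these scales between baseline and 6 months post-treatment will be determined for both therapy groups and the groups compared to each other". No method is named there.
- **Protocol summary** lists ARAT, NIHSS and "Quality of life assessment: EQ-5D questionnaire" as secondary measures. UEFM points do not appear.
- **Section 6.0 (analysis plan)** reads "Secondary outcome measures for the trial are ARAT test, , NIHSS, and EQ-5D". A little further on it says "Absolute difference (in points) in improvement will be summarized for both treatment groups between baseline and 5-10 days" and at the later visits, with "the treatment groups compared via a two-way ANOVA". It names no scale, factors or baseline covariate.
- **Section 6.4 (strata and covariates)** describes additional models for the binary primary endpoint and for "absolute changes (in points) in the tests of motor function (UEFM, and ARAT) using hours of occupational therapy outside the trial". These models also use total therapy hours, over the treatment phase and the 6 months of follow-up.
- **Section 6.1** refers the detailed methods to a separate statistical analysis plan (version 1.0, 06 August 2018).

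**The concern.** The UEFM is the primary scale, and its change in points is the natural companion to the 5-point responder result. Section 1.1 reports the pilot on this scale (mean gains of 13.8 and 7.1 points). Section 6.1 makes the Bayesian analysis that borrows NICHE active-arm data the primary one and uses E-FIT-only data to show robustness. A clean randomised comparison of UEFM points is a useful part of that support.

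As the protocol stands, two careful analysts could differ on three things: whether UEFM points is a pre-specified secondary outcome, whether the two-way ANOVA applies to it, and whether its model contains therapy hours. Those choices should not remain open on the primary scale once data are seen.

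**Working it through.** **The plan's own figure.** The only sizing is for the responder endpoint: 81% power with 60 patients. The usual normal approximation is

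power = Φ{[|p1 − p0|√n − 1.96√(2p̄(1 − p̄))] / √[p1(1 − p1) + p0(1 − p0)]}, with n = 30 per arm and p̄ the mean of p1 and p0.

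- 84% vs 50%: (0.34 × 5.477 − 1.96 × 0.665) / 0.620 = 0.90, so power is 81.6%.
- 72% vs 36%: (0.36 × 5.477 − 1.96 × 0.705) / 0.657 = 0.90, so power is 81.5%.

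The stated figure reproduces. It says nothing about the points outcome, for which the protocol gives neither an SD nor a power. The rest of the check is textual.

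**Step 1: the three lists.**

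| Outcome | 3.2 | Summary | 6.0 |
|---|---|---|---|
| UEFM change in points | yes | no | no |
| ARAT | yes | yes | yes |
| NIHSS | yes | yes | yes |
| EQ-5D | yes | yes | yes |

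The lists disagree on UEFM points alone.

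**Step 2: does the ANOVA in 6.0 cover UEFM?** The sentence follows the list without UEFM, which suggests it does not. But it speaks of improvement in points, close to the wording of the UEFM item in 3.2, and is not restricted to the listed scales. Section 6.0 also opens by comparing functional motor tests between groups, and section 5.2.5 counts the Fugl-Meyer among the functional tests. Both readings are open.

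**Step 3: what is the ANOVA?** One factor is presumably treatment. The other could be visit, time-since-stroke stratum or site. The choice matters: with visit as the second factor, each patient contributes up to four correlated changes and the 6-month contrast is only one part of the model. With stratum, the model can be fitted at 6 months alone.

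**Step 4: baseline.** No baseline term is mentioned. If baseline and 6-month scores have equal variance σ² and correlation ρ, the change score has variance 2σ²(1 − ρ), and the baseline-adjusted outcome has variance σ²(1 − ρ²). Their ratio, adjusted to unadjusted, is (1 + ρ)/2, which never exceeds 1. Adjustment also deals with chance baseline imbalance, which is plausible at about 30 per arm. The protocol gives no ρ, so the gain cannot be quantified.

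**Step 5: section 6.4.** Under section 5.2.6, therapy hours are collected during treatment and follow-up, after randomisation. Recovery may change how much therapy a patient seeks. A model conditioning on those hours does not estimate the plain effect of assignment, so it cannot stand in for the main comparison.

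**The case against.** A reader might infer that the plan leaves UEFM points out of the analysis, or that the therapy-hours model is the only one intended. The documents do not support either inference. The ANOVA sentence can be read as covering UEFM and has no therapy-hours covariate. Section 6.4 presents its models as additional, which presupposes base analyses, and treats the binary primary endpoint in the same sentence. Naming UEFM points there suggests, if anything, that a points analysis was intended. The double comma in the 6.0 list may mark a lost entry, so that omission should not be pressed hard; the list in the protocol summary shows no such gap. The separate SAP may settle the model.

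A reader might also want to size the point by comparing the power of a points analysis with that of the responder test, using the cited 1 Hz effect size of 0.69. That would measure the cost of dichotomising, which the fix leaves in place. The effect size is for motor outcome across trials and is not specific to UEFM.

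It can also be said that ANCOVA is a preference, since a two-way ANOVA is a valid class of model. That is fair as far as it goes. But an ANOVA with unnamed factors is not yet a specification, and baseline adjustment uses data already collected.

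What remains is the disagreement between the lists and the incomplete description of the model.

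**Conclusion.** The point holds as an inconsistency and an under-specification. UEFM change in points is a declared secondary outcome in one place and absent from two other lists. The protocol does not say whether its two-way ANOVA applies to it, what the factors are, or whether baseline enters. The only model tied to it by name uses post-randomisation hours and is labelled additional.

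Its size is modest: one secondary outcome, with no bearing on the primary endpoint or on the 60 patients planned. No numerical effect is claimed. The conclusion rests on the protocol text alone. If the separate SAP already gives a clear model, what is left is to bring the protocol into line with it. The case for baseline adjustment rests on standard theory, with equal variances assumed in the formula above.

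**What to change.** 1. Keep the responder endpoint as primary.
2. List UEFM change in points from baseline to 6 months as a secondary outcome in the protocol summary and section 6.0, matching section 3.2.
3. State its main analysis in 6.0: ANCOVA comparing the arms in the randomised E-FIT ITT population, with baseline UEFM and the time-since-stroke stratum (3-6 vs 6-12 months), without therapy hours and without borrowed NICHE patients. Report the mean difference and 95% CI beside the responder result.
4. If the two-way ANOVA stays for ARAT, NIHSS and EQ-5D, name the scales and both factors.
5. Keep the section 6.4 therapy-hours models, labelled as supportive only.
6. Check the separate SAP and make its wording agree.

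The cost is a wording change in the protocol and SAP and one model on data already collected. The primary endpoint, visits and sample size do not change. The changes should be made before unblinding.

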4.1. SELECTION OF SUBJECTS

This trial will include volunteers who meet eligibility criteria and agree to participate in the study. The purpose of the study including risks and benefits will be explained to potential participants who will then be asked to sign an informed consent form. Potential participants will be screened for inclusion and exclusion criteria.

60 patients will be randomized to the study (for rationale see section 6.1 Power analysis). Additional subjects may be recruited to compensate patients lost from follow-up or withdrawn from the study.

4.2. SUBJECT SELECTION CRITERIA

Candidates for this study must meet ALL of the following inclusion criteria and NONE of the exclusion criteria:

Inclusion Criteria :

- ≥ 18 years of age
- An ischemic stroke suffered 3-12 months prior to the study;
- no other known brain abnormalities by history;
- A one-sided stroke resulting in upper extremity paresis
- A Chedoke–McMaster Stroke Assessment arm stage and hand stage of 3-6 for the affected limb

Exclusion Criteria

- Implanted metallic parts of implanted electronic devices, including pacemakers, defibrillators, or implant medication pump;
- Pregnant or trying to become pregnant; Lack of pregnancy established in females of child-bearing potential by a negative urine pregnancy test at screening.
- Active alcohol abuse, illicit drug use or drug abuse or significant mental illness
- Patients suffering from depression as measured by a score of ≥ 10 on the Patient Health Questionnaire (PHQ9). For clarity, patients diagnosed with depression which is controlled with stable anti-depressive medication and in whom PHQ9 is <10 are eligible to participate in the trial.
- History of epilepsy, defined as at least two unprovoked seizures occurring greater than 24 hours apart or diagnosis of an epilepsy syndrome, and no seizures within the last 12 months.
- Any condition that would prevent the subject from giving voluntary informed consent;
- An implanted brain stimulator;
- Any metal in head with the exception of dental work or any ferromagnetic metal elsewhere in the body ;
- Enrolled or plans to enroll in an interventional trial during this study;
- Scalp wounds or infections;

- Claustrophobia precluding MRI;
- A fixed contraction deformity in the affected limb that would prevent normal dexterity if patient were neurologically intact;
- Excessive spasticity as indicated by the Modified Ashworth Spasticity (MAS) Scale >2/4 in either elbow flexors, wrist flexors or finger flexors of the affected limb
- previous stroke with residual deficits (TIAs not a reason for exclusion);
- premorbid (retrospective) modified Rankin Scale (mRS) score ≥ 2 of any aetiology;
- a concurrent progressive neurologic disorder, acute coronary syndrome, severe heart disease (NYHA Classification ≥ 3), or other major medical condition,
- confirmed or suspected lower-limb fracture preventing mobilization,
- patients requiring palliative care
- patients planning to undergo any other occupational therapy during the 6 week active treatment period of the trial (see section 5.2 for study schedule) than what is provided in the study
- A recent injection of botulinium toxin to the affected upper limb in the last 3 months, or the need of an injection of botulinum toxin anytime during the study period and follow up.
- A recent injection of phenol to the affected upper limb in the last 6 months, or the need of an injection of phenol anytime during the study period and follow up.
- Ataxia as measured by a score ≥ 1 on item 7 (limb ataxia) of the NIH stroke scale.
- Severe sensory deficits as measured by a score of 2 on item 8 of the NIH stroke scale.
- Severe aphasia as measured by a score of ≥ 2 on item 9 (best language) of the NIH stroke scale.
- Severe neglect as measured by a score of 2 on item 11 (extinction and inattention) of the NIH stroke scale.
- Patients unable to comprehend or follow verbal commands
- Based on PI's or local physician's assessment patient unable to tolerate the trial procedure due to medical condition
- A Mini mental status exam (MMSE) <25.

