5.2. VISIT SCHEDULE

The study will be performed over 24 to 29 sessions:

- 1) Visit 1(Screening visit): Baseline = 3-12 months after the stroke. The purpose of this visit is to obtain informed consent for the study (if not previously obtained) and to screen subjects for inclusion and exclusion criteria.
- 2) Visit 2: Baseline assessment. The purpose of this visit is to establish the baseline of injury, motor status and NBS parameters (Localization of cortical motor representation area of the target muscle to which therapeutic rTMS will be subsequently delivered, see appendix A). Subjects will also undergo a structural MRI. The subject will then be randomized to either rTMS or to sham treatment. The baseline visit may if necessary take place on 2 separate days.

- 3) Visits 3-20: During these visits the patient will undergo standardized task-oriented motor rehabilitation of the hand. In addition the patient will receive the rTMS therapy according to the protocol of the group she/he was randomized into during visit 1. The visits will take place during a 6 week period, three visits per week. During each week the visits will take place each on a separate day and a maximum of two visits will take place on consecutive days.
- 4) Visit 21: End of the task-oriented motor rehabilitation. The purpose of the visit is to establish the extent of recovery that has occurred during the rehabilitation. The visit will take place 5-10 days after the last rTMS/rehabilitation session and includes functional motor testing).1-2 visits may be needed to complete assessment.
- 5) Visit 22: 1month (±5 days) after the end of the rehabilitation therapy. The purpose of the visit is to determine whether any changes in motor function have occurred within 1 month of ending therapy. The assessment includes functional motor testing. 1-2 visits may be needed to complete assessment.
- 6) Visit 23: 3 months (±5 days) after end of the rehabilitation therapy. The purpose of this visit is to determine whether any changes in motor function or NBS parameters have occurred within 3 month of ending therapy. The assessment includes functional motor testing. In patients experiencing a new stroke, only the data prior to the event will be used in the analysis. 1-2 visits may be needed to complete assessment.

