5.2.1 Screening and informed consent

Eligibility will be confirmed through a series of steps as follows (see inclusion/exclusion criteria for details).

- Medical history and medications.
- The Modified Rankin Scale (MRS) assessed by interview will used to determine functional ability prior to the stroke.
- The Modified mini mental exam (MMSE) [Teng and Chui 1987] is a series of questions (approximately 5 minutes) to assess orientation (e.g. date, place) and ability to follow commands.
- Spasticity will be measured using the Modified Ashworth Spasticity (MAS) Scale [Bohannon and Smith 1987]. The MAS is a 6-point ordinal rating scale for measuring muscle tone, with ratings from 0 (no increase in tone) to 4 (limb rigid in flexion or extension).
- The National Institutes of Health Stroke Scale (NIHSS) is a measure of neurological functioning, with higher scores reflecting greater deficit (maximum 42).
- Chedoke-McMaster Stroke Assessment (CMSA) [Gowland et al. 2003] includes an impairment inventory and an activity inventory. The Impairment inventory includes staging assessments of shoulder pain, postural control, recovery of arm and hand, and recovery of leg and foot. Only arm and hand impairment will be assessed which stages each between 1 and 7 with higher score indicating better motor performance
- The possible presence and severity of depression will be assessed using the Patient Health Questionnaire (PHQ9) [Graves & Bobardier 2008]. The PHQ9 has nine inquiries about the frequency of symptoms associated with depressed mood over the

previous 2 weeks, each scored between 0 (not at all) to 3 (nearly every day). The maximum score is 27 points. Scores that equal 10 or greater are associated with clinical depression. The PHQ9 has been tested and validated in stroke populations with good sensitivity for detecting depression [de Man-van Ginkel, et al. 2012; Janneke, et al. 2012].

Structural MRI

Unless already existing, an MRI will be acquired using a high resolution (1.5T or more) T1 weighted image of the subject's brain on any standard magnetic resonance system. MRI acquisition parameters and instructions are shown in the NBT System User manual.

The subject's structural MRI sliced images will be loaded into the Nexstim NBT system.

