5.2.2 Baseline assessment

The following functional tests will be administered by an experienced researcher. Training and certification of the researchers to perform these tests is described in a separate Outcome Assessment Training and Certification Plan

- The *Fugl Meyer (FM)* will measure functional movement. The FM offers impressive test-retest reliability (total=.98-.99; subtests=.87-1.00), and construct validity [Duncan et al. 1983; DiFabio and Badke 1990]. The upper extremity (UE) FM movement scale is a measure of upper limb function, with higher scores reflecting greater function.
- The Action Research Arm Test (ARAT) [Lyle 1981] is used to determine whether fine • motor skill changes occurred in the affected hand and fingers. The ARAT is a 19-item test divided into four categories (grasp, grip, pinch, and gross movement), with each item graded on a 4-point ordinal scale (0=can perform no part of the test; 1=performs test partially; 2=completes test but takes abnormally long time or has great difficulty; 3=performs test normally) for a total possible score of 57. The test is hierarchical in that, if the patient is able to perform the most difficult skill in each category, he/she will be able to perform the other items within the category and, thus, they need not be tested. The ARAT has high intrarater (r = .99) and retest (r = .98) reliability and validity [Lvle] 1981 Van der Lee et al 20011
- *The National Institutes of Health Stroke Scale* (NIHSS) will be repeated at baseline visit.
- *EQ-5D*

The EQ-5D questionnaire is a standardized, well validated instrument for assessing patients' health and quality of life. The questionnaire will be utilized to establish the overall impact of stroke on the patients' quality of life and used to assess possible changes during the trial period.

Diagnostic NBS-TMS session:

• motor mapping of the healthy hemisphere, and determination of motor threshold and the optimal cortical representation area of the muscle of interest

(m.Extensor Digitorum Communis, m.EDC), The NBS protocol is described in detail in appendix A.

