6.3 ANALYSIS POPULATIONS

Intent-to-Treat (ITT) Population

The ITT population will consist of all randomized subjects. Subjects in the ITT population will be summarized and analyzed in the treatment group to which they were randomized, regardless of the treatment they actually received.

Per Protocol (PP) Population

The PP population will consist of all subjects who were randomized, received study treatment, and had no major protocol violations.

If a subject suffers a new stroke during the trial and the new stroke affects the motor function of the limb being treated in the study, only the outcome assessment data collected prior to the new stroke will be used for PP Population analysis. The sponsor will review the new strokes and determine if it affects the motor function of the limb.

Safety Population

The Safety population will consist of all subjects who received study treatment. Subjects in the safety population will be summarized and analyzed according to the treatment they actually received, regardless of whether or not they were randomized to receive that treatment.

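### No eligibility rule ensures that a randomised patient has the 5 points of Fugl-Meyer headroom needed to be a responder; the cost is uncertain and possibly nil, but the check is cheap

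*Combined protocol and SAP*

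**What the plan says.** - **Eligibility (4.2).** The inclusion list asks for "A one-sided stroke resulting in upper extremity paresis" and a Chedoke–McMaster "Stroke Assessment arm stage and hand stage of 3-6 for the affected limb". Section 5.2.1 explains that this instrument "stages each between 1 and 7 with higher score indicating better motor performance". Stage 7 is therefore excluded, and stage 6 in both arm and hand is eligible. No inclusion or exclusion criterion uses the UEFM.
- **Endpoint (Protocol Summary; 3.1; 6.0).** "Minimal clinically important improvement is defined as an increase of 5 points on the upper extremity Fugl-Meyer score". The primary comparison is the proportion of patients reaching this between baseline and 6 months post-treatment.
- **Scale (5.2.2).** The UEFM is described as one "with higher scores reflecting greater function". Its maximum is not stated, and nothing relates Chedoke stage to UEFM score.
- **Timing (5.2, 5.2.2).** UEFM is a baseline assessment, and the Visit 2 entry continues: "The subject will then be randomized to either rTMS or to sham treatment". The next entry (Visits 3–20) instead places randomisation at Visit 1.
- **Analysis (6.1, 6.3, 6.4).** "The ITT population will consist of all randomized subjects", and this is the primary population. Stratification is by time since stroke; the additional covariates are therapy hours. Baseline UEFM is in neither list. The primary efficacy analysis is Bayesian and borrows 88 ischaemic active-arm patients from NICHE; E-FIT alone is the supporting analysis.

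**The concern.** Eligibility is set on one instrument and success on another, bounded one. A patient whose baseline UEFM is within 4 points of the maximum cannot gain 5 points under any treatment, and so counts as a failure in whichever arm he or she falls. Such a patient uses one of 60 places, lowers that arm's response rate and says nothing about rTMS on the primary endpoint. With a binary endpoint and stated power of 81%, there is little slack.

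The borrowed comparison raises a separate issue. Randomisation balances these patients on average within E-FIT, but nothing balances them between E-FIT and NICHE.

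**Working it through.** **Inputs from the plan.** About 30 per arm, 1:1 (5.2.3); two-sided 0.05 (6.5); planning rates 84% v 50% (pilot) and 72% v 36% (NICHE ischaemic active arm v NICHE investigators' expectation); 118 v 30 after borrowing; stated power 81% and 96% (all 6.1).

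**Assumption.** The share c of randomised patients without 5 points of headroom is not given. I take c = 0, 3, 5 and 10%, the same in both arms.

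**1. The plan's own figures.** The pooled-variance normal approximation at 30 v 30 gives 81.6% (84/50) and 81.5% (72/36), against 81% stated. At 118 v 30 it gives about 96% for both pairs, against 96% stated. The stated power reproduces.

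**2. Method.** Power is computed exactly: the binomial probabilities of all outcome pairs for which the Pearson chi-square rejects are summed. At c = 0 this gives 82% for both pairs at 30 v 30. The Wald test named in section 6.0 gives 80.4% and 82.1%, so the choice of test matters little.

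**3. Two readings of the planning rates p.**
- *Rates include such patients.* The stated power stands, and excluding them raises each rate to p/(1−c). At c = 5%: 0.84/0.95 = 0.884 and 0.50/0.95 = 0.526.
- *Rates do not include them.* Each true rate is p(1−c). At c = 5%: 0.84 × 0.95 = 0.798 and 0.50 × 0.95 = 0.475.

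Exact power, 30 v 30:

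| c | 84/50, included, then excluded | 84/50, not included | 72/36, included, then excluded | 72/36, not included |
|---|---|---|---|---|
| 0 | 82% | 82% | 82% | 82% |
| 3% | 86% | 78% | 85% | 80% |
| 5% | 89% | 75% | 86% | 78% |
| 10% | 95% | 69% | 90% | 73% |

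**4. Borrowed layout, 118 v 30, pessimistic reading p(1−c).** This is a frequentist proxy, because the Bayesian method is in a separate analysis plan cited in 6.1 that is not in the reviewed document.

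| c | 84/50 | 72/36 |
|---|---|---|
| 0 | 97% | 96% |
| 3% | 95% | 94% |
| 5% | 93% | 93% |
| 10% | 89% | 90% |

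**5. Bias in the pooled comparison.** If the share differs between the trials by d, and patients with headroom respond at rate r, the pooled active rate shifts by (88/118) × d × r. For illustration, d = 10 points and r = 72% give 0.746 × 0.10 × 0.72 = 0.054, about 5 points, with no treatment effect. If d = 0, the shift is zero.

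**6. Effect of filtering NICHE.** Patients without headroom are all non-responders, so removing them changes 72% to 0.72/(1−c), that is 74%, 76% or 80% at c = 3, 5 or 10%. About 85, 84 or 79 of the 88 patients remain.

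**The case against.** The strongest objection is that no such patient may exist. Paresis is required and both arm and hand are capped below the top Chedoke stage, which is a real upper limit on function. Without the UEFM maximum or a Chedoke–UEFM link, the documents cannot show that a stage 6 patient lies within 4 points of the top. This stands, and it is why the range must start at zero.

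Second, section 1.1 describes the NICHE population as otherwise the same apart from also admitting haemorrhagic stroke. The observed 72% therefore probably already includes any such patients, and scaling it down again would count them twice on the active side. This also stands: the pessimistic 72/36 figures are a bound. The 36% is an expectation, so whether it includes them is unknown.

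Third, 30 v 30 is the supporting analysis, and the loss in the borrowed layout is smaller. That is correct, and both are shown.

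Fourth, absolute UEFM change is a secondary outcome (3.2) that does not depend on the threshold. That is partial mitigation; it does not alter the primary endpoint. The separate analysis plan may adjust for baseline UEFM, but adjustment cannot make a patient without headroom able to respond.

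A reader might infer that near-normal patients will be enrolled in number, that the stated power is wrong, or that the randomised comparison is biased. The documents support none of these: the share is unknown, the stated power reproduces, and within E-FIT such patients fall equally in both arms on average.

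**Conclusion.** The gap is real: eligibility does not guarantee the headroom that the endpoint requires, and intention to treat makes any patient without it a certain non-responder. Its size rests on an assumed share of 0–10%. At zero nothing changes. Otherwise exclusion helps under either reading of the planning rates. At 30 v 30 and shares of 3–10%, it adds about 3 to 13 points to the 82% if the rates include such patients, or avoids a loss of about 2 to 13 points if they do not. In the borrowed layout the avoided loss is about 1 to 7 points from 96–97%.

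The tempting headline, that power falls to 69%, needs a 10% share, the 84/50 rates, planning rates free of such patients, and the supporting analysis rather than the primary one. Bias arises only in the pooled comparison and only if the share differs between NICHE and E-FIT; nothing in the documents shows that it does. This is a cheap improvement with a modest and uncertain gain.

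**What to change.** - Add to 4.2: baseline UEFM, measured at Visit 2 and checked before randomisation, must be at least 5 points below the scale maximum. State the maximum.
- Correct the Visits 3–20 entry in 5.2, which places randomisation at Visit 1, so that the check clearly precedes allocation.
- Apply the same filter, using baseline scores only, to the 88 NICHE active patients. Fix it before E-FIT is unblinded. Because NICHE outcomes are already known and the filter can only raise the borrowed active rate, report the unfiltered borrowing result as a sensitivity analysis.

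The cost is a few screen failures at Visit 2, slightly fewer than 88 borrowed patients, and a claim that no longer covers patients with almost no deficit. If no patient lacks headroom, the criterion removes no one.
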